Recruitment for the study will have two methods. The primary method begins by screening for CB use during enrollment with the quitline and assessing eligibility and interest in the study. Optum's computer system will provide initial pre-screening so that only callers from participating quitlines who are 21+ years old are screened for the study. Registration agents will ask additional screening questions including CB use for at least 9 days in the last 30, interest in quitting smoking within 30 days, ready access to phone and email, screen negative for serious mental illness (schizophrenia), and whether they have an interest in study participation. The secondary recruitment method will be recruiting from ads on location specific social media sites (e.g., the r/Washington site on Reddit). Interested participants will email the study research assistant who will screen participants over the phone and enroll them into their respective state quitline if eligible. All participants will be contacted by phone by research-trained coaches who will describe the study in more detail, obtain informed consent, and deliver the baseline assessment and the post-randomization script.

Additionally, after the baseline assessment participants will be randomly assigned to receive the standard QL intervention (TAU) or the integrated intervention (QL-CBCU). All participants will receive the follow-up assessment (outcomes) survey at 3 months.

7. Enrollment / Consent Plan and Materials

Research-trained coaches will describe the study in more detail, read the information/consent document verbatims- and obtain verbal informed consent.

8. Compensation/Remuneration/Reimbursement

Incentives

Participants will receive \$30 after completing call 1 (for the baseline assessment and call 1 participation), \$20 for completing the second coaching call, \$50 for completing the follow-up survey or \$25 for a partially completed follow-up survey or a brief survey in lieu of the full follow-up survey, and \$20 for completing the biochemical validation test. Participants will also have an option to complete the online survey within 48 hours of the email informing them to complete the survey for an additional \$25 bonus. These incentives will be provided to all participants and both study groups (TAU and QL-CBCU). A randomly selected group of participants in the experimental group will be invited to complete a post intervention interview with the PI or the Co-I and receive \$25 upon completion.

6. STUDY PROCEDURES

1. Procedures

Quitline registration agents at Optum will screen incoming callers from participating QLs for CB use and other study eligibility criteria or the study research assistant will screen interested participants recruited from social media ads. Specially trained QL (RIU Check-UP) coaches deliver the informed consent script. They complete the baseline assessment over the phone with participants who give their verbal consent to participate in the study. Participants are randomized to the standard QL treatment as usual (TAU) or the experimental treatment (QL-CBCU), which is provided by the RIU Check-UP coaches.

We will email participants a link to the follow-up survey (with instructions) at 3 months post enrollment. For those who do not complete the online survey after two emails, we will send participant contact information via a secure transmission protocol to an external survey group, Maryland Marketing Source (MMS; blind to study condition) who will attempt to complete the survey by phone, making up to 11 attempts at different times of day and on different days. Those who do not complete the interview within 14 days may be emailed a reminder to complete the full online follow-up survey or an optional brief survey in lieu of the full follow-up survey. Our research team will monitor completed surveys to identify those who reported they had not smoked tobacco in the past 7 days and request a biochemical validation test from participants as explained below. Selected participants will be contacted after completing the follow-up survey for an interview via Microsoft Teams or Zoom about their experience with the intervention. Participants will be provided with the link and dial in number for Teams or Zoom to access the interview and be notified the call may be recorded or transcribed. If the participant objects to a Zoom or Teams interview, they may be offered a phone interview as an alternative. If a participant engages in inappropriate or abusive behavior towards the study team, they may be terminated from the study by the Principal Investigator.

Biochemical verification:

Participants self-reporting tobacco abstinence 7 or more days at follow-up will be sent a test to confirm their abstinence by biochemical verification (saliva). Before sending the biochemical verification kit, study staff may contact the participant via email with an alert that a biochemical verification kit with instructions will be mailed to them and can be tracked with the provided USPS tracking number. A cover letter will be included in the kit explaining how to complete the test, instructions for returning the results via a photo to the study team's email box, and 14 day requested timeline for submitting the results. Instructions in the kit will inform participants to not eat or drink 10 minutes prior to taking the saliva test. Participants will be directed to refrain from including any PII in this email. If the results are not received within 7 days of delivery, a follow up email reminder may be sent. If the test outcome is returned by the participant, study staff will send the participant a \$20 gift card for their participation (regardless of test outcome).

2. Subject Participation

Participant experience in the study:

Day 1.

SCREENING- Participant will answer questions if interested in study participation.

- INFORMED CONSENT If interested and eligible, participant will hear the consent form read to them by the Quit Coach. The participant may ask questions before giving their consent. The Quit Coach will note the participant has provided their verbal informed consent. The participant will be mailed a copy of the consent.
- **BASELINE SURVEY** Participant will spend approximately 20 minutes answering baseline assessment questions.
- FIRST COACHING CALL Participant will engage in coaching call about quitting smoking with some discussion of how cannabis use will affect their quit attempt. Afterwards they will be sent a gift card for \$30.
- **EMAIL PFR** Participant will be sent a feedback report based on their answers to the assessment questionnaire.
- COACHING CALL 2 Participant will be contacted by phone second coaching call which will focus on interaction of tobacco and cannabis and the feedback report. Participant will be paid \$20 following this call.

FOLLOW UP COACHING CALLS. Participants will be contacted for 2-3 more calls to discuss how their smoking quit is going and follow up on cannabis use and goals. 2/3 months following enrollment:

- **Survey**: Participant will be emailed follow up survey which will take about 5 minutes for the brief and 20-30 minutes for the full to complete online. If participant does not complete online, a phone survey company will call and deliver the survey by phone. If not reached by phone, participants may be mailed a reminder to complete the full online survey or a brief online survey. Participants will receive a \$50 gift card for completing the full survey or \$25 for a partially completed full survey or the brief survey. If participants complete the outcomes survey within 48 hours of the email sent informing them about the survey, they will receive an additional \$25 bonus for completion.
- **Biochemical Verification**: If participant reports being quit from tobacco at follow up, a saliva test will be sent for confirmation. Participants will receive a small package containing all materials and instructions. After completing the test, they will take a picture of the test strip and send to the study team via email. They will receive a \$20 gift card for completing the test and sending a picture within 14 days
- **Interview**: Selected participants may agree to a phone interview. The research team will call selected participants to schedule an interview via Teams or Zoom. Questions will concern the participants experience and opinions about the intervention. This will take less than an hour, and they will receive a \$25 gift card for the interview.

Control group only

Participant experience in the study - the control group participants will receive standard QL services and are eligible for the same gift cards but will not receive the marijuana use-related materials (PFR) or treatment (coaching call content). They will not be invited to participate in any qualitative interviews.

3. Participant Engagement & Results

All counseling calls will be attempted at least five times over different days. We will increase retention at the 3 month follow up survey by reminding participants during coaching calls, notifying participants by email that their survey is due, and offering the survey first via email with a link to the online survey. For those who do not complete the online survey, we will have an external survey company attempt to reach participants by phone, making 11 attempts to reach them on different days and at different times. Finally, if participants have not responded to the phone survey, we may email participants a reminder via email containing links to take the full online survey or optional brief survey. We may follow up with participants who only partially

completed the survey online to troubleshoot any issues completing the survey online offer opportunity to complete survey by phone. Participants will receive an invitation for a post intervention interview with the PI or Co-I and receive \$25 upon completion, for a total of up to \$145 in incentives. Strategies such as these have proven to be effective in our quitline research studies resulting in higher recruitment and retention rates.

4. Data Collection

The sources of research materials obtained from individual human subjects in the study are limited to records and data, which will be available to the study team. Records include number and duration of counseling calls automatically collected by Optum. Data will be in the form of self-report questionnaires collected on the phone or via the internet and stored in a secure computer assisted telephone interview (CATI) system or via a secure link to a survey collection database. The follow-up survey may be completed via an online secure survey sent by Optum or telephone survey conducted by an external survey team. There will also be biochemical verification of tobacco use at 3 months post randomization. Documentation of verification will be provided to the study team by the participant in the form of a de-identified picture of the test result.

5. Data Analysis

For the proposed pilot study we plan to use summary statistics (means and proportions) with confidence intervals (CIs), and standard errors (SE), and graphical displays (histograms, pie charts, Box plots, etc.), as appropriate, to describe participant self-reported demographic characteristics, use of tobacco and cannabis, and other tobacco and cannabis variables measured at baseline and/or at each coaching call and at 3-months. We will use Fisher's exact tests, t-tests, and Wilcoxon rank sum tests to compare intervention and control groups. Comparisons including mean number of calls completed, mean satisfaction ratings, mean change in cigarettes per day (CPD), and mean change in days of cannabis use will be completed. We also will compare groups on changes over time on other cannabis measures, including hazardous cannabis use. We will address the effect of missing values on estimated smoking cessation rates using sensitivity analyses for outcome measures: 1) we will analyze responders only, and 2) we will impute missing tobacco use as 'smoking'.

We will have sufficient power with 100 participants (50 per group) and a 70% response to the follow-up interview to detect significant effects of the integrated intervention (vs. standard treatment controls) on feasibility and acceptability of the QL-CBCU intervention as measured by calls completed and treatment satisfaction at 3 months. This sample size is also sufficient for estimating QL-CBCU's potential impact (compared with the standard quitline) measured at 3 months on tobacco abstinence and CB outcomes (motivation to reduce days using CB, confidence in avoiding CB over-use, decreased problems associated with CB use, and decreased frequency of use). The sample sizes for this feasibility study are sufficient for the conduct and reporting of stage I pilot studies and were not selected for purposes of detecting statistically significant group differences at the alpha .05 level on outcomes. Our sample size is sufficient for documenting what power is available. For ordinal measurements that can statistically be treated in a similar manner to "continuous" measures (such as the number of QL calls completed and days used CB), we have 80% power to detect an effect size of 0.68. For proportions, we are powered to detect a difference in proportions of 0.22 to 0.34 (depending on the proportions in the two groups).

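### Only the outside phone-survey vendor is stated to be blind; the saliva-strip photos that decide verified abstinence go to a study team with no masking of arm described

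*Combined protocol and SAP*

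**What the plan says.** Section 6.1 (Procedures) describes the vendor that makes the follow-up survey calls as "blind to study condition". This is the only blinding statement in the document.

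The verification route is spread over sections 6.1, 6.2 and 6.4. The research team reviews completed surveys to find those reporting 7-day abstinence, and a saliva kit is mailed to them. On completing the test, "they will take a picture of the test strip and send to the study team via email". Section 6.4 (Data Collection) adds: "Documentation of verification will be provided to the study team by the participant in the form of a de-identified picture of the test result". On privacy, section 6.1 says: "Participants will be directed to refrain from including any PII in this email". A reminder to those who have not returned a result within 7 days of delivery is optional. No reader is named, and no rule is given for reading a strip or rejecting a photo.

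On knowledge of arm, section 5.8 (Compensation) draws interviewees at random from the experimental group, and section 6.2 has the research team call them to schedule. Of the controls it says: "They will not be invited to participate in any qualitative interviews".

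On incomplete online surveys, section 6.3 says "We may follow up with participants who only partially" finished the survey, in order to troubleshoot and "offer opportunity to complete survey by phone".

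**The concern.** By using a blind vendor for the survey calls, the sponsor accepts that knowing the arm could colour outcome collection. The verified outcome does not pass through that vendor. It depends on staff deciding what a photographed strip shows, whether the photo is usable, and whether to chase a result that has not arrived. Each step allows some judgement, and a reader who knows the arm could favour one group without meaning to.

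Biochemically verified cessation is named among the 3-month outcomes in section 2, and it is the result a reader will treat as objective. Section 8.4 says the findings may support funding for a fully powered trial. Reading cannot be masked after the event, so the step has to be settled before strips come in.

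**Working it through.** **1. Who handles each outcome route, and is masking stated?**

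| Route | Who handles it | Masking stated? |
|---|---|---|
| Online survey | Participant, unaided | Not needed for entry |
| Phone survey | External vendor (4.3, 6.1, 6.2, 6.3, 6.4) | Yes (6.1) |
| Strip photo | Study team (6.1, 6.2, 6.4) | No |
| Reminder for an unreturned strip | Not specified; optional (6.1) | No |
| Phone completion after a partial online survey | Team may offer it; caller not named (6.3) | Not stated for this step |

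**2. Does de-identification mask arm?** No. Leaving personal details out of the email and photo protects privacy. The result must still be tied to a participant for the \$20 payment and for analysis, and nothing hides arm at that link.

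**3. Does the team know arm?** Some of it must. Interviews are restricted to one arm and the research team schedules them. Section 6.1 places interviews after the follow-up survey, so they can overlap with the return of strips. The document does not say that the same people read the strips.

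**4. Denominators.** The plan gives no figure on this point, so its sample-size figures are used. Section 6.5 has 50 per group and 70% response, which gives 50 × 0.70 = 35 responders per arm. A two-sample t-test at 35 per arm, two-sided alpha 0.05 (sidedness assumed) and 80% power detects 0.679, so the stated 0.68 reproduces. Section 5.2 allows up to 230 participants: 230 / 2 = 115 per arm, and 115 × 0.70 = 80.5 responders.

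**5. Effect of one changed reading on an arm's verified rate, 1/n.**

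| Total randomised | Missing counted as smoking | Responders only |
|---|---|---|
| 100 | 1/50 = 2.0 points | 1/35 = 2.9 points |
| 230 | 1/115 = 0.9 points | 1/80.5 = 1.2 points |

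For scale, section 6.5 gives detectable differences of 22 to 34 points. At 35 per arm, one reading is 2.9/34 = 9% to 2.9/22 = 13% of that.

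**6. How many strips would be read?** The document gives no expected abstinence or photo-return rate. Assume 15% to 35% of responders report abstinence.
- 100 randomised, every photo returned: 100 × 0.70 × 0.15 = 10.5 to 100 × 0.70 × 0.35 = 24.5.
- 100 randomised, 70% of photos returned (assumed): 10.5 × 0.70 = 7.4 to 24.5 × 0.70 = 17.2.
- 230 randomised, every photo returned: 230 × 0.70 × 0.15 = 24.2 to 230 × 0.70 × 0.35 = 56.4.

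**7. Illustration with assumed counts.** Fisher's exact p is 0.090 for 15/50 against 7/50 and 0.034 for 17/50 against 7/50. This needs two readings changed in the same direction in one arm. Its 17 + 7 = 24 verified quitters sit at the top of the range in step 6. It shows sensitivity and is not a forecast.

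**8. Unreturned strips.** Section 6.5 counts missing tobacco use as smoking in one sensitivity analysis, but does not say how an unreturned strip is treated. If it also counts as smoking, uneven reminders would shift verified rates even with every strip read correctly.

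**The case against.** A reader might infer two stronger things.

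The first is that unmasked staff will take survey answers by phone from partial responders. The document does not establish this. Section 6.3 says the team may offer phone completion and does not say who makes the call. Wherever the document names who conducts phone surveys, it is the external company. The same section also uses the first person plural for work given to that company. The natural reading is that the team offers and the vendor calls, so only a confirmation is needed.

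The second is that the strip readers know arm. That is also not stated. The interviews themselves are done by the principal investigator or a co-investigator, section 8.1 gives the call recordings for fidelity work to university co-investigators, and the photos go to a study mailbox. The readers could be other people.

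Further points also have force. The document reports no rate of ambiguous strips. The counts in step 6 rest on assumed rates, and the effect per strip more than halves at the ceiling of 230. Section 6.5 says the sample was not chosen to detect significant differences. Section 9 mentions a procedures manual, not available here, which may already cover the reading.

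These points limit the size of the concern. They do not supply masking for the strip step, where the plan names the study team and says nothing about arm.

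**Conclusion.** The point holds for the strip photos, at low severity. Stated blinding covers the survey vendor alone, the photos go to a team of which at least some members know arm, and removing identifiers does not mask arm. That the readers know arm is a possibility the plan leaves open, and no actual bias is alleged. The survey-call question is a clarification and not a finding.

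The size is 2.0 points per changed reading at 50 per arm and about 0.9 points at 115 per arm. Both assume equal allocation and that missing results, including unreturned strips, count as smoking. How many readings could change cannot be estimated from the document. Severity stays low because the aims are feasibility, acceptability and a preliminary effect, and most self-report comes online or through the blind vendor.

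**What to change.** - **Reading.** Save each photo under study ID only. Have an existing team member who has no access to allocation, and no part in interviews or fidelity work, read it and judge whether it is readable. Record the result before it is merged with arm. Another staff member can file the emails and send the gift card, since payment does not depend on the result.
- **Reminders.** Send the 7-day reminder to every non-returner in both arms instead of leaving it optional.
- **Clarification.** Confirm that the blind vendor calls partial online responders who accept phone completion, as the other text on phone surveys implies.

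The cost is a small file-handling step, a sentence or two of procedure wording and a slight delay in processing results. It assumes that one current team member can be kept away from allocation. It needs no new staff or extra participant visits.

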2. STUDY PURPOSE & OBJECTIVES

Our specific aims are to:

- Develop an integrated tobacco/cannabis (CB) intervention utilizing key components of the Marijuana Check-up (MJCU, a brief behavioral intervention for increasing motivation to reduce or quit using cannabis). We will adapt the MJCU intervention for integration into tobacco cessation counseling; develop the intervention manual and training materials, and pilot test the new treatment with 10 QL callers who use CB. Our team includes an author of the MJCU, [name] at the University of Washington who will assist with development, training, and implementation of the integrated intervention.
- 2) Conduct a small, randomized pilot trial of the integrated intervention compared with the standard QL (treatment as usual; TAU) to evaluate feasibility, acceptability, and preliminary effectiveness with 100 co-users recruited from 4 participating state QLs. We will assess implementation factors, coach fidelity, treatment engagement, and outcomes at 3 months (satisfaction, tobacco cessation (biochemically verified), and CB use).

We hypothesize that the intervention will: (1) be feasible to deliver (measured by coach treatment fidelity scores); (2) be acceptable to co-users (measured by enrollments and call completion numbers); (3) increase tobacco cessation rates compared with TAU; (4) increase co-users' motivation to change CB use; and (5) will produce greater reduction or cessation of CB.

Significance: This study comes at a critical time to answer key questions posed by state and local health departments who are considering the best methods for reaching CB users and increasing treatment utilization. Nationally, QLs have expressed concerns about the potential growth of co-users calling quitlines and the need to address the impact this has on treatment outcomes.

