4. STUDY DESIGN

1. Design

D.4. Phase 2: Preliminary effectiveness pilot randomized controlled trial.

Overview. QL registration agents, coaches and/or research staff at Optum will screen for CB use and other study eligibility criteria and enroll participants into their respective state quitline. Once confirmed eligible, consented participants will complete the baseline assessment and be randomized into standard QL treatment as usual (TAU) or the experimental treatment, QL-CBCU. Approximately 3 months after randomization, we will email participants a link to the follow-up survey (with instructions). For those who fail to complete the online survey after two emails, we will send participant contact information via a secure transmission protocol to an external survey group who will attempt to complete the survey by phone, making 11 attempts at

different times of day and on different days. Those who do not complete the interview within 14 days will be emailed a reminder to take the full online survey or an optional brief online survey. Our research team will monitor completed surveys to identify those who reported they had not smoked tobacco in the past 7 days and request a biochemical validation test from participants as explained below (See section D.8.2. Biochemical Validation).

D.4.1. Setting. Participants will primarily be recruited from incoming callers from four state tobacco QLs with fully legalized CB use (Alaska, Washington DC, Oregon, Washington). See letters of support. These four QLs offer four or five proactive coaching calls, mailed support materials, access to text messaging, and web-based programs, plus at least two weeks of free NRT. If recruitment rates are slow, an alternative strategy of recruiting from social media (e.g., Reddit) will be implemented. All eligibility criteria will remain the same.

There will be two behavioral interventions tested in this trial; the standard quitline (treatment as usual: TAU) and the standard QL plus an adapted version of the CBCU (QL-CBCU). Both are phone based, brief, and utilize similar behavior change techniques: motivational interviewing (MI) and cognitive behavioral therapy (CBT). Both interventions include 4-5 proactive counseling calls, mailed materials, and at least 2 weeks of NRT. The new QL-CBCU intervention is being designed to be integrated into the quitline setting and delivered by quitline coaches with minimal training and infrastructure adaptation.

1. Duration

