Participation will take about 3 months. The entire duration of the study is approximately 3 years.

Table 2. Self-Report Measures	Screen	Baseline	3-month follow-up
Demographics	Х	Х	
Chronic Conditions and Health Problems	Х		
Mental Health (PhQ2, GAD, PSS)		Х	
Alcohol Use		Х	
TO & E-Cigarette Use	Х	Х	Х
Motivation for Quitting TO		Х	
Cessation Medication use			Х
CB Use		Х	
Marijuana Problem List (MPL) & CUDIT		Х	Х
Motivation for Quitting/Reducing CB Use	Х		Х
CB Quit Goals and Impact on TO Use	Х		Х
Outcomes			
Program satisfaction and acceptability (usefulness,			v
would recommend the program to others)			^
7- and 30-day point prevalence tobacco			×
abstinence			~
Cannabis use (days/ week; occasions/day; hours		Х	X
of intoxication)		~~~~~~~~~~~~~~~~~~~~~~~~~~~~~~~~~~~~~~~	

2. Metrics and Variables

3. Data

The sources of research materials obtained from individual human subjects in the study are limited to records and data, which will be available to the study team. Records include number and duration of counseling calls automatically collected by Optum. Data will be in the form of self-report questionnaires collected on the phone or via the internet and stored in a secure computer assisted telephone interview (CATI) system or via a secure link to a survey collection database. The 3-month follow-up survey may be completed via an online secure survey sent by Optum or telephone survey conducted by an external survey team. For participants who do not respond to the online or phone surveys, the research team will email participants a reminder to complete the full online survey or an brief online survey. There will also be biochemical verification of tobacco use at 3 months post randomization.

4. Materials

Emailed and mailed letters An emailed outcomes survey Saliva test kit

5. Devices – N/A

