Research findings will be disseminated as peer-reviewed publications and conference presentations. If applicable, findings may be used to secure funding for additional research and a fully powered randomized trial.

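### Does the plan's silence on unreturned saliva tests leave the tobacco cessation analysis undefined?

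*Combined protocol and SAP*

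**What the plan says.** The aims (section 2) list "outcomes at 3 months (satisfaction, tobacco cessation (biochemically verified), and CB use" as what the pilot will assess. Table 2 in section 4 is a table of self-report measures, and its outcome rows include "7- and 30-day point prevalence tobacco" abstinence.

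The biochemical verification text in section 6 sets out the procedure: "Participants self-reporting tobacco abstinence 7 or more days at follow-up will be sent a test to confirm their abstinence by biochemical verification (saliva"). The participant emails a photograph of the result. For a late test the provision is "If the results are not received within 7 days of delivery, a follow up email reminder may be sent". Payment does not depend on the result: "If the test outcome is returned by the participant, study staff will send the participant a" $20 card. None of this says how a failed or unreturned test is scored. The design text in section 4 refers the reader on with "See section D.8.2. Biochemical Validation", but no section carries that number.

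The data analysis text (section 6, item 5) gives two sensitivity analyses for the cessation rate: "1) we will analyze responders only, and 2) we will impute missing tobacco use as" smoking. It does not mention saliva, verification or tests. Section 8, item 2 only points back to it.

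**The concern.** A verified outcome can be missing in two ways: the survey is not answered, or the survey is answered and the test does not come back. The plan's rules visibly address only the first. The second can happen only to people who said they had quit.

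If responders means people with a complete verified outcome, the responders-only analysis discards quitters with no test and keeps all self-reported smokers who answered. If missing tobacco use includes a missing test, the same people count as smokers. If neither rule reaches the test, the analysis is of self-report and not of the outcome in the aims. No reading is named as the lead.

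The publication plan (section 8, item 4) says "findings may be used to secure funding for additional research and a fully powered randomized trial", so a quit rate that depends on an unstated rule could be carried into the design of the next study.

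**Working it through.** **The plan's own figures.** With 50 per group and 70% response, 35 per group are analysed. A two-sided 5% t-test with 35 per group has power 0.801 at an effect size of 0.68, so the stated 80% reproduces. For proportions, the pooled formula at 80% power gives detectable differences from 0.22 (2% control rate) up to 0.33. Fisher's exact test gives 0.22 (0% control rate) up to 0.36. The stated 0.22 to 0.34 is approximately reproduced. The power statement thus counts survey responders, which bears on what the word means.

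**What the text means by response.** The power paragraph in the data analysis text attaches its 70% to the follow-up interview. Section 6, item 3 speaks of not having responded to the phone survey. In both places a responder is someone who answered the survey. A self-reported quitter with an unreturned kit has answered it and stays in the denominator.

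**How far the readings differ.** The documents give no quit rate and no test-return rate, so these are assumptions: self-reported quitting p = 25% (control) and 35% (QL-CBCU), return r = 60%, every returned test confirming. Survey response s = 70% is the plan's figure.

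| Reading | Formula | Control % | QL-CBCU % | Difference | Ratio |
|---|---|---|---|---|---|
| A: self-report, survey responders | p | 25.0 | 35.0 | 10.0 | 1.40 |
| B: self-report, missing = smoking | p·s | 17.5 | 24.5 | 7.0 | 1.40 |
| C: verified, survey responders, unreturned = not quit | p·r | 15.0 | 21.0 | 6.0 | 1.40 |
| D: verified, all randomised, any missing = not quit | p·r·s | 10.5 | 14.7 | 4.2 | 1.40 |
| E: verified, unreturned dropped | p·r / [1 − p(1 − r)] | 0.15/0.90 = 16.7 | 0.21/0.86 = 24.4 | 7.8 | 1.47 |

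For return between 40% and 80%, the difference runs 4.0 to 8.0 points for C, 2.8 to 5.6 for D and 6.0 to 9.1 for E.

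- With equal return in both arms, A to D shrink the absolute difference but leave the risk ratio at 1.4.
- E, the reading that drops quitters, lands close to the planned analysis B (16.7 v 24.4 against 17.5 v 24.5). In simulation at 50 per arm, the readings disagree on direction in 21% of datasets whether or not E is included.
- C and D, the pair that the aims and the two rules point to, disagree on direction in about 2% of simulated datasets, with a mean spread of 3.0 points.

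**Against sampling error.** The 95% half-width of a difference is 1.96·√[2p(1 − p)/n], using the control rate in both arms.
- A, n = 35: 1.96·√(2·0.25·0.75/35) = 20.3 points.
- D, n = 50: 1.96·√(2·0.105·0.895/50) = 12.0 points.
- At 115 per arm (230 in all), multiply by √(50/115) = 0.659: 13.4 and 7.9 points.

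The widest gap in the table, A to D, is 10.0 − 4.2 = 5.8 points, below every one of these.

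**Unequal return.** With no true difference, p = 25% in both arms and return of 70% v 50%:
- A and B give 0.
- C gives 0.25 × 0.20 = 5.0 points.
- D gives 5.0 × 0.7 = 3.5 points.
- E gives 0.175/0.925 − 0.125/0.875 = 4.6 points.

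Any handling of the verified outcome is distorted by a similar amount, so fixing the rule in advance would not remove this.

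**The case for a change.** The best argument for a change is that the rule for missing tobacco use does not plainly cover someone who answered the tobacco question and then did not return a kit. Both rules are called sensitivity analyses, yet no main cessation analysis is named. The data analysis text also says the sample suffices to estimate the potential impact on abstinence, so that quantity ought to be defined. A follow-on trial sized on A needs 329 per arm and one sized on D needs 979.

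Part of this stands. The plan does not say which definition leads, or how failed and unreturned tests are classified. Nor does it say what counts as confirming in someone still using nicotine replacement, which is offered in both arms. An analyst must supply these.

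The rest is weaker. The sample-size contrast mixes denominators: 329 counts survey responders, which at 70% response is 329/0.7 = 470 randomised per arm, so the ratio is 979/470, about 2.1 and not 3. A full trial would also choose its own endpoint. Table 2 does not contradict the aims: self-reported abstinence belongs in a table of self-report measures, and section 4 separately states that verification will be done. The D.8.2 pointer looks like leftover numbering, since the same text uses D.4 and D.4.1, and the procedure it promises is in section 6.

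**Conclusion.** No change to the plan follows. This is missing detail that analysts would fill sensibly; no stated rule produces a wrong result. The aims name verified cessation, the data analysis text supplies two rules for survey non-response, and together they lead to C and D, with unreturned tests kept in the denominator as not verified. Self-report and test results are both collected, so A and B and the return counts by arm can be reported beside them.

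Counting unreturned tests as not quit is itself a trade-off. It understates quitting if non-returners really quit (by a factor of 0.6 at 60% return), and it creates a false difference of 3.5 to 5.0 points if return were 70% v 50%. Nothing in the documents suggests such a gap, and the kit, the reminder provision and the $20 card apply to both arms.

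On the assumed rates, the choice of reading moves the difference by at most 5.8 points, against half-widths of 12.0 to 20.3 points at 50 per arm. The plan itself says the sample was not chosen to detect group differences on outcomes. The conclusion rests on taking response to mean survey response, on the assumed quit and return rates, and on return being similar in the two arms.
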